**Objectives:**

Through a research questionnaire and pre-procedure baseline testing of strength, sensory, NRS pain score and post procedure testing of strength, sensory, and NRS pain score we will obtain data regarding cervical epidural steroid injections via a transforaminal approach using corticosteroid to determine if the proposed hypothesis listed below is supported and if the null hypothesis will be rejected.

**Hypothesis:** Targeted cervical epidural steroid injections via a transforaminal approach using corticosteroid superior to targeted injections using an epidural catheter via an interlaminar approach with particulate steroid for improving pain and function in patients with cervical radicular pain.

**Null Hypothesis:** Targeted cervical epidural steroid injections via a transforaminal approach with non-particulate corticosteroid will provide no difference in pain relief or functional improvement as compared to targeted injections using an epidural catheter via an interlaminar approach with particulate steroid in patients with cervical radicular pain.

**Introduction**

Cervical radicular pain is a common, disabling problem that occurs in 83:100,000 individuals per year. Symptoms are most often caused by intervertebral disc herniation (21.9%) or central or foraminal stenosis from spondylosis (68.4%). Patients complain of pain in the head, neck, scapula, or arm. The diagnosis of radicular pain is made clinically by history and physical examination, supported imaging studies, and electrodiagnostic tests.

In the absence of a progressive neurologic deficit, initial treatment of cervical radicular pain includes oral anti-inflammatory medications, activity modification, postural retraining, ergonomic adjustments, and physical therapy. If this conservative approach fails to relieve pain, an image guided epidural steroid injection (ESI) is the second-line treatment. Corticosteroids act primarily through the inhibition of the phospholipase A2-initiated arachadonic acid cascade, thereby reducing local inflammation and intraneuronal edema and enhancing blood flow around the affected nerve root. Steroids also suppress transmission of nociceptive C-fibers via direct membrane stabilizing effects.

Though well-conducted prospective, randomized controlled trials of CESI are few in number, a systematic review of the literature demonstrates that CESI is clinically effective in treating radicular pain. When cervical epidural steroid injections were compared to intramuscular steroid injections in a clinical trial, 68% of patients treated with interlaminar cervical epidural

steroid injections had significant pain relief at one year follow-up, compared to only 11.8% of the patients receiving intramuscular injections. In another study, cervical epidural steroid injections were successful in reducing pain in 80% of patients with a mean follow up period of 43 months. In another clinical trial, however, only 20-26% of patients with disc herniation who failed non-interventional care experienced good to excellent results after cervical ESI. Prospective, randomized, controlled studies have shown that ESI reduces the rate of spinal surgery in the lumbar spine, and there is evidence of a similar effect related to cervical ESI.

Two distinct techniques used to administer epidural steroids specifically to the nerve root affected in a radicular pain syndrome, which include transforaminal access at the level of pathology and interlaminar interlaminar access at the C7-T1 level with subsequent advancement of an epidural catheter to the level of pathology. Use of an epidural catheter is necessary in order to achieve a targeted injection via an interlaminar approach in order to prevent dural puncture or direct spinal cord trauma. Anatomic studies confirm the distance between the ligamentum flavum and dura is on average, 4 mm at the C7-T1 or C6-C7 levels, but 1mm or smaller at C5-C6 and more rostral levels. Therefore, there is likely greater risk of dural puncture and spinal cord injury when “targeting” steroid delivery using only the interlaminar technique directly at the level where pathology is located (C4-C5, or C5-C6, for example). Thus, the interlaminar placement of a needle rostral to the C6-C7 level has been strongly discouraged.

Both the transforaminal injection approach and the targeted catheter approach demonstrate effectiveness. Studies have demonstrated the effectiveness of transforaminal epidural steroid injection for the treatment of cervical radicular pain. Our own recent work demonstrates the clinical effectiveness of the catheter-based targeted approach. However, these two approaches have never been directly compared. Thus, we aim to compare the differences in pain reduction, medication utilization, functional outcomes, patient satisfaction, and surgical rate reduction between these two approaches to the treatment of cervical radicular pain.

Cervical radicular pain is a common syndrome, often treated with epidural steroid injection (ESI). An approach that targets the therapeutic agent, corticosteroid, at the site of spinal pathology can be performed via a transforaminal approach or via a interlaminar approach at C7-T1 with subsequent epidural catheter advancement to the symptomatic level. There are no universal guidelines that recommend the use of one technique over the other. We will directly compare the clinical effectiveness of these two approaches as measured by pain reduction, medication utilization, functional outcomes, patient satisfaction, and surgical rate reduction. The results of this study will potentially influence clinical practice recommendations regarding the treatment of cervical radicular pain. If one technique proves superior, instituting this technique will have implications potentially for reducing opioid use, surgery and other healthcare utilization, and general healthcare cost related to the treatment of cervical radicular pain.

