## **Study design:**

### **Prospective, randomized, comparative trial**

Patients will be randomized to group #1 or #2 based on a random computer-generated schedule.

Group #1: Transforaminal cervical ESI with dexamethasone sodium phosphate 1.5 mL (10mg/mL) and 1 ml 1% lidocaine (total volume 2.5 mL).

Group #2: Catheter-targeted ESI via interlaminar access at the C7-T1 level with triamcinolone acetonide 2 mL (40mg/mL) and 1 ml 1% lidocaine (total volume 3 mL).

Dexamethasone will be used in the transforaminal group, while triamcinolone will be used in the catheter-based group as this represents the standard of care for performing these injections, consistent with current safety recommendations.

Adults who are eligible and scheduled to have an epidural steroid injection for cervical radicular pain at the University of Utah Orthopaedic Center will be approached by authorized research personnel. All eligible patients will be offered to participate in the study and all patients will sign a written informed consent form before proceeding and will also be consented for the procedure. Participating in the study is voluntary. The patients may choose not to enroll in the research. Patients will be presented with the same options of treatment whether they enroll or decide not to.

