### *Transforaminal epidural steroid injection*

After injection of 1 to 2 mL of 1% lidocaine to the skin and subcutaneous tissues, a 25-gauge spinal needle will be placed at the level and side of radicular pathology, based on clinical

correlation of symptoms/signs and magnetic resonance imaging findings. Advancement to the appropriate target position in the neuroforamen will be performed under fluoroscopic guidance according to practice guidelines. Once a satisfactory target position is achieved and confirmed in both anterior-posterior and oblique views, 0.5 to 1 mL of contrast (Omnipaque-240; GE Healthcare, Princeton, New Jersey) will be injected under live fluoroscopic observation with or without digital subtraction angiography depending on suggestion of vascular uptake, as is standard practice and recommended by practice guidelines. Upon confirmation of a satisfactory epidural contrast pattern without vascular uptake, the injectate will be delivered: dexamethasone sodium phosphate 1mL (10mg/mL) and 0.5 ml of 1% preservative-free lidocaine (total volume 1.5 mL). After the injection procedure, participants will be observed and then discharged from the clinic with written discharge instructions (current standard practice).

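### Route and steroid are fully confounded, so the trial can compare the two route-plus-steroid packages but cannot credit a result to technique alone, as the stated aim, implication and trait modelling do

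*Combined protocol and SAP*

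**What the plan says.** The Study design section fixes one steroid to each route and gives the reason: "Dexamethasone will be used in the transforaminal group, while triamcinolone will be used in the catheter-based group as this represents the standard of care". The sentence goes on to cite current safety recommendations. The Procedures subsections repeat the pairing, and the Repeat injections subsection keeps the randomised injection for any repeat. No participant is therefore assigned either route with the other steroid.

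The question is worded differently in different places:

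- **Introduction.** The two techniques are described by how the epidural space is reached, and the aim is a comparison of the two approaches. The closing paragraph treats corticosteroid as one generic agent and then says: "If one technique proves superior, instituting this technique will have implications potentially for reducing opioid use". Neither paragraph mentions that the steroids differ.
- **Objectives, working hypothesis.** The transforaminal arm carries only the generic word: "via a transforaminal approach using corticosteroid superior to targeted injections using an epidural catheter". The catheter arm is specified as particulate.
- **Objectives, null hypothesis.** Steroid class is named on both sides, with the first arm given as "transforaminal approach with non-particulate corticosteroid".
- **Statistical analysis.** Groups are compared by t test, chi-square or Fisher exact test. Modelling then looks for patient traits that favour one technique over the other.

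No section says that conclusions are limited to the combination of route and steroid, or that the two effects cannot be separated.

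**The concern.** A two-arm trial yields one contrast per outcome. Here that contrast carries two differences at once, the route and the drug. If the transforaminal arm does better, the cause could be the route, the steroid, or both. If the arms look alike, the two effects may be absent or may be cancelling. Text that speaks of technique alone invites the report to credit the route with the whole result, and the data cannot bear that out.

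The trait modelling inherits the problem. A trait that appears to predict benefit from one technique may be predicting response to one steroid.

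**Working it through.** **Inputs.** Two arms with one steroid per route (Study design; Procedures; Repeat injections). Recruitment of 50 per group, with 40 per group expected after 20% attrition (Power Analysis). Primary outcome: proportion with at least a 50% NRS reduction at 1 month (Data Analysis Plan). The documents give no responder rates, so those used below are assumptions.

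**The plan's own figure.** 40 / (1 − 0.20) = 50 per group, 100 in total. This reproduces. The 40 itself cannot be derived, because no effect size or target power is stated.

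**Identifiability.** Let R = 1 for transforaminal and 0 for catheter, and S = 1 for dexamethasone and 0 for triamcinolone. For every participant S = R. The matrix with columns (1, R, S) has two identical columns, so its rank is 2, not 3. Without an interaction, the arm difference estimates only the sum

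δ = r + s,

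where r is the route effect and s the steroid effect. In percentage points, δ = 20 arises equally from (r, s) = (20, 0), (0, 20) or (35, −15), and δ = 0 arises from (0, 0) or (15, −15). Larger samples sharpen δ but never split it. Any interaction between route and drug is absorbed into δ as well. In the trait modelling, trait × R and trait × S are likewise the same column.

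A 2×2 crossing of route and steroid would have rank 3. That only shows what identification would require; it is not a proposal to change treatments.

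**Illustration of size.** Assume no route effect, 50% responders in one arm, 40 per group and two-sided 5%. With p̄ the mean of p₁ and p₂, the approximate power of the two-proportion test is

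Φ{ [ |p₂ − p₁| − 1.96 √(2p̄(1 − p̄)/n) ] / √( [p₁(1 − p₁) + p₂(1 − p₂)]/n ) }.

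For 50% against 70%, p̄ = 0.60. The null term is 1.96 × √(0.48/40) = 0.2147 and the denominator is √(0.46/40) = 0.1072. Then (0.20 − 0.2147)/0.1072 = −0.137, and Φ = 0.445.

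Probability of a significant result when the steroid alone causes the difference:

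- 10 points: 14%
- 15 points: 27%
- 20 points: 45%
- 30 points: 82%

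Each such result would be a true finding about the packages and a wrong one if reported as a route effect.

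**Is the package itself defined?** Study design gives the first arm as "Group #1: Transforaminal cervical ESI with dexamethasone sodium phosphate 1.5 mL (10mg/mL) and 1 ml 1% lidocaine (total volume 2.5 mL"), whereas Procedures gives "dexamethasone sodium phosphate 1mL (10mg/mL) and 0.5 ml of 1% preservative-free lidocaine (total volume 1.5 mL"). For the second arm, Study design has "Catheter-targeted ESI via interlaminar access at the C7-T1 level with triamcinolone acetonide 2 mL (40mg/mL) and 1 ml 1% lidocaine (total volume 3 mL"), whereas the catheter subsection has 1 mL of the same triamcinolone concentration with 0.5 mL lidocaine, 1.5 mL in all. In milligrams of steroid:

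- Study design: 1.5 × 10 = 15 mg dexamethasone; 2 × 40 = 80 mg triamcinolone
- Procedures: 1 × 10 = 10 mg dexamethasone; 1 × 40 = 40 mg triamcinolone

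Under Study design the total volumes also differ between arms (2.5 against 3 mL), which makes volume a further component tied to route. Under Procedures they are equal (1.5 mL each).

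**The case against.** The strongest reply is that the package is the right unit. The plan states that each steroid is paired with its route as standard of care, so a clinician who adopts a route on that basis adopts its steroid too. Randomisation gives a valid estimate of that practical choice. The pairing is open, the null hypothesis already describes it, and the working hypothesis lacks a single qualifier. The Introduction's implication is hedged background text, not an estimand or a reporting rule. The documents offer no estimate of a difference between the two steroids, so the practical size of the problem is unknown.

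Most of this stands. It rules out three stronger readings that a reader might infer. The first is that the trial cannot answer any useful question; the package comparison is sound. The second is that the hypotheses concern technique alone; the null names steroid class in both arms and the working hypothesis names it in one. The third is that the plan commits to instituting the better technique; it speaks only of potential implications if one proves superior.

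The reply does not reach the Introduction's own definition, which identifies the techniques by route and leaves the steroid generic, or the trait modelling, which repeats the term. A good reason for using different steroids does not make a route-only inference valid. If the package is what is meant, the plan does not say so where it states its aim.

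**Conclusion.** The point holds as a limit on what may be concluded. The confounding is complete (rank 2 of 3), follows from the assignment alone and needs no numerical assumption. No planned analysis can repair it. What the trial can support is a statement about transforaminal injection with dexamethasone against catheter-targeted injection with triamcinolone.

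How far a route-only reading would mislead cannot be determined from the documents. The 14% to 82% range rests on an assumed 50% responder rate, 40 per group, no route effect and steroid differences of 10 to 30 points. These are not false-positive rates for the planned test, which remains valid for the packages. The need for a change is about wording and interpretation, not allocation, sample size or the tests. The conflict over injectate amounts is a separate contradiction, but it leaves the package undefined until it is resolved.

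**What to change.** Keep the arms and make these changes:

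1. **Objectives.** Name the steroid class for the transforaminal arm in the working hypothesis so that it matches the null. The contrast in the null can stay as it is.
2. **Introduction.** Reword the aim and the closing implication as a comparison of transforaminal injection with dexamethasone and catheter-targeted injection with triamcinolone.
3. **Data Analysis Plan.** State that conclusions apply to the two packages only, and that no difference or absence of difference will be attributed to route or steroid alone.
4. **Statistical analysis.** Replace technique with the named packages in the trait modelling.
5. **Study design and Procedures.** Reconcile the steroid amounts, lidocaine amounts and total volumes so that each package has one definition. Which description is correct is for the investigators to settle.

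Items 1 to 4 are wording only and leave recruitment and the planned tests unchanged. The price is a narrower claim: the report could recommend a package but could not say that one route is better than the other.

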## Subjects

A total of 100 subjects, aged 18-80 on the day of enrollment, will be recruited for participation in this study. Patients will be randomized to one of two groups based on a random computer-generated schedule.

Those assigned to Group #1 will undergo a transforaminal cervical ESI and those in Group #2 will receive a catheter-targeted ESI via interlaminar access at the C7-T1 level.

#### De-identification

All subjects will be assigned a unique alphanumeric identifier. No personally identifiable information will be used in the final database. All data will be stored on a highly secure, password protected computer.

#### Participant Recruitment

Our intended subject demographic includes an active population between the ages of 18 and 80 years on the day of enrollment. We intend to recruit participants primarily through word-of-mouth and from a database or participant pool for which participants have given prior permission to be contacted for research studies. Additionally, recruiting will take place through the distribution of flyers to the Health Sciences Education Building, University of Utah Student Life Center, the University of Utah Orthopaedic Center, and the University of Utah hospital. Upon first contact with the potential participant, the study coordinator or research associate will provide a basic description of the study and review inclusion and exclusion criteria, general health status, and past and current athletic participation. Interested volunteers who qualify will be asked to report to the University of Utah Orthopaedic Center. Prior to screening procedures and after being informed of any potential risks involved in the study, volunteers will be asked to provide written, informed consent for study participation.

#### Inclusion Criteria:

- 1) Age 18-80.
- 2) Clinical diagnosis of unilateral C4-C8 radicular pain.
- 3) Magnetic resonance imaging pathology consistent with clinical symptoms/signs.
- 4) Numerical Rating Scale (NRS) pain score of 4 or higher.
- 5) Pain duration of more than 6 weeks despite trial of conservative therapy (medications, physical therapy, or chiropractic care).

#### Exclusion criteria:

- 1) Refusal to participate, provide consent, or provide follow-up information for the 6-month duration of the study.
- 2) Contraindications to Cervical ESI (active infection, bleeding disorders, current anticoagulant or antiplatelet medication use, allergy to medications used for CIESI, and pregnancy).
- 3) Cervical spinal cord lesions; cerebrovascular, demyelinating, or other neuro-muscular muscular disease.
- 4) Current glucocorticoid use or ESI within past 6 months.
- 5) Prior cervical spine surgery.
- 6) Patient request for or requirement of conscious sedation for the injection procedure.

## **Study design:**

### **Prospective, randomized, comparative trial**

Patients will be randomized to group #1 or #2 based on a random computer-generated schedule.

Group #1: Transforaminal cervical ESI with dexamethasone sodium phosphate 1.5 mL (10mg/mL) and 1 ml 1% lidocaine (total volume 2.5 mL).

Group #2: Catheter-targeted ESI via interlaminar access at the C7-T1 level with triamcinolone acetonide 2 mL (40mg/mL) and 1 ml 1% lidocaine (total volume 3 mL).

Dexamethasone will be used in the transforaminal group, while triamcinolone will be used in the catheter-based group as this represents the standard of care for performing these injections, consistent with current safety recommendations.

Adults who are eligible and scheduled to have an epidural steroid injection for cervical radicular pain at the University of Utah Orthopaedic Center will be approached by authorized research personnel. All eligible patients will be offered to participate in the study and all patients will sign a written informed consent form before proceeding and will also be consented for the procedure. Participating in the study is voluntary. The patients may choose not to enroll in the research. Patients will be presented with the same options of treatment whether they enroll or decide not to.

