## **Procedures**

During the injection procedure, the participant will be positioned on a fluoroscopy table. Blood pressure and pulse oximetry monitors will be placed. A pre-procedure time-out will be performed, as is protocol in the University practice. Vital signs will be recorded immediately prior to and every 5 minutes during the injection procedure as is the current practice standard. Using fluoroscopic guidance, cervical ESI using one of the two approaches based on group randomization will be performed:

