#### *Catheter-targeted ESI via interlaminar access at the C7-T1 level*

After injection of 1 to 2 mL of 1% lidocaine to the skin and subcutaneous tissues, an 18-gauge 3.5-inch RX Epidural Needle (Epimed International Inc., Dallas, TX) will be placed at the C7-T1 level per practice guidelines and current safety recommendations, and a loss of resistance (saline) technique will be used to gain access to the epidural space; needle position will be confirmed in anteroposterior and lateral views. A radiopaque styled 21-gauge epidural catheter (C-KATH; Epimed International Inc., Dallas, TX) will be introduced through the Tuohy needle and advanced under live image guidance to the level and side of radicular pathology, based on clinical correlation of symptoms/signs and magnetic resonance imaging findings. Once a satisfactory target position is achieved with the catheter, 0.5 to 1 mL of contrast (Omnipaque-240; GE Healthcare, Princeton, New Jersey) will be injected. Upon confirmation of a satisfactory epidural contrast pattern, the injectate will be delivered: triamcinolone acetonide 1 mL (40mg/mL) and 0.5 ml 1% lidocaine (total volume 1.5 mL). After the injection procedure, participants will be observed for 20 to 30 minutes and then discharged from the clinic with written discharge instructions (current standard practice).

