#### **Data Collection:**

An electronic data collection sheet (via iPad) will be used to record all pre-procedure data (see data collection sheet):

- 1) Age (years).
- 2) Sex.
- 3) Height (cm).
- 4) Weight (Kg).
- 5) Duration of pain (weeks).

- 6) Location of cervical radicular pain based on clinical diagnosis: C2, C3, C4, C5, C6.
- 7) Radiologic diagnosis based on MRI of the Cervical Spine.

Before an initial injection, the following measures will be obtained:

- 7) NRS for pain; separate scores for neck pain and for arm pain
- 8) Neck Disability Index (NDI-5)
- 9) Medication Quantification Scale (MQS III) score
- 10) Daily opioid use in morphine equivalents

Immediately after injection the following will be obtained:

- 11) Fluoroscopy time
- 12) Post-injection NRS pain score; separate scores for neck pain and for arm pain
- 13) Adverse events, if they occurred

At intervals of 2 weeks, 1 month, 3 months, 6 months, and 1 year after injection, outcome measurements will be repeated. The Patient Global Impression of Change (PGIC) and a patient satisfaction score (five-point Likert scale: 1, very dissatisfied; 2, dissatisfied; 3, neither satisfied nor dissatisfied; 4, satisfied; and 5, very satisfied) will also be recorded. A single researcher blinded to group assignment collected all follow-up assessments in person, by e-mail, by telephone, or by mailed questionnaire.

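### The protocol gives two conflicting injectates for each randomized arm (steroid dose, lidocaine dose and total volume) and does not say which applies

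*Combined protocol and SAP*

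**What the plan says.** The injectate is specified twice for each arm, and both versions are current text.

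- **Transforaminal arm (Group 1).** *Study design: Prospective, randomized, comparative trial* gives "dexamethasone sodium phosphate 1.5 mL (10mg/mL) and 1 ml 1% lidocaine (total volume 2.5 mL"). *Procedures: Transforaminal epidural steroid injection* gives "dexamethasone sodium phosphate 1mL (10mg/mL) and 0.5 ml of 1% preservative-free lidocaine (total volume 1.5 mL").
- **Catheter arm (Group 2).** The same Study design section gives "triamcinolone acetonide 2 mL (40mg/mL) and 1 ml 1% lidocaine (total volume 3 mL"). *Procedures: Catheter-targeted ESI via interlaminar access at the C7-T1 level* gives "triamcinolone acetonide 1 mL (40mg/mL) and 0.5 ml 1% lidocaine (total volume 1.5 mL").

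Three other places bear on which version applies:

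- The sentence that opens Procedures says that "cervical ESI using one of the two approaches based on group randomization will be performed".
- Study design justifies the drug used in each arm "as this represents the standard of care for performing these injections, consistent with current safety recommendations".
- *Repeat injections* requires any repeat to be the same injection as the one assigned, allows at most two repeats, and states no dose.

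**The concern.** The injectate is part of what defines each randomized treatment. An operator who follows Study design departs from Procedures, and the reverse. Adherence to the assigned treatment therefore cannot be judged from this document, and a reader could not report or replicate the tested regimen from it.

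The two versions also describe different comparisons. The arms already differ in route and in steroid type. Under one version they differ in injected volume as well, and under the other they do not. The steroid doses change by different fractions in the two arms, so choosing a version also shifts the relative steroid dose between arms.

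**Working it through.** **Inputs.** Volumes and steroid concentrations come from the four quoted specifications. The one conversion not printed in the protocol is that 1% lidocaine contains 10 mg/mL (1 g per 100 mL).

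**Step 1: reproduce the stated totals** (steroid mL + lidocaine mL).

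- Group 1, Study design: 1.5 + 1 = 2.5 mL, as stated.
- Group 1, Procedures: 1 + 0.5 = 1.5 mL, as stated.
- Group 2, Study design: 2 + 1 = 3 mL, as stated.
- Group 2, Procedures: 1 + 0.5 = 1.5 mL, as stated.

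All four add up. A single misprinted or misread digit would have broken a sum.

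**Step 2: doses per injection** (mL × mg/mL) and the change from Study design to Procedures.

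| | Study design | Procedures | Change |
|---|---|---|---|
| Group 1 dexamethasone | 1.5 × 10 = 15 mg | 1 × 10 = 10 mg | 1 − 10/15 = 33% lower |
| Group 1 lidocaine | 1 × 10 = 10 mg | 0.5 × 10 = 5 mg | 1 − 5/10 = 50% lower |
| Group 1 volume | 2.5 mL | 1.5 mL | 1 − 1.5/2.5 = 40% lower |
| Group 2 triamcinolone | 2 × 40 = 80 mg | 1 × 40 = 40 mg | 1 − 40/80 = 50% lower |
| Group 2 lidocaine | 1 × 10 = 10 mg | 0.5 × 10 = 5 mg | 1 − 5/10 = 50% lower |
| Group 2 volume | 3 mL | 1.5 mL | 1 − 1.5/3 = 50% lower |

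**Step 3: contrast between arms.**

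- Volume, catheter to transforaminal: 3/2.5 = 1.20 under Study design and 1.5/1.5 = 1.00 under Procedures.
- Triamcinolone to dexamethasone, mg per mg: 80/15 = 5.33 under Study design and 40/10 = 4.00 under Procedures, so the ratio changes by a factor of 4.00/5.33 = 0.75. A fixed potency factor k gives (40k/10)/(80k/15) = 0.75, so k cancels.

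**Step 4: look for text that reconciles the versions.**

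- The 1 to 2 mL of lidocaine for skin and subcutaneous tissue is a separate, earlier step. The disputed lidocaine sits inside the injectate and its total.
- The standard-of-care rationale explains which drug each arm receives, not how much.
- Repeat injections adds no second dose level. It carries the same ambiguity into the repeats.
- No section gives a dose range, leaves the dose to the operator, notes an amendment or says which section prevails.

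**The case against.** The best reply is that Procedures is the operative text. Its opening sentence ties the injection to the randomized group and ends in a colon that leads straight into the two step-by-step descriptions, each with a full recipe. Study design can then be read as a summary. That reading is plausible and narrows the ambiguity in practice. It is not stated, however. The opening sentence itself ties only the approach to randomization, and Study design is where the randomized groups are defined.

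A second reply is that little harm is shown. Route and drug are the same in both versions. The hypotheses set the arms apart by approach and steroid type, with no mg or mL. The primary outcome, the tests and the sample size do not depend on dose. The documents attach no clinical meaning to the 0.75 ratio and do not show that 0.5 mL of volume matters. All of this stands, and it limits the claim to an unspecified intervention. It does not remove the conflict.

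A third reply concerns recording the dose actually given. The items listed under "Immediately after injection the following will be obtained" are fluoroscopy time, pain scores and adverse events, with no dose or volume. But Data Collection refers to a separate form ("An electronic data collection sheet (via iPad) will be used to record all pre-procedure data (see data collection sheet"), which is not in the documents and may capture it. That objection is fair, so recording is a conditional add-on and not part of the main point.

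**Conclusion.** The concern holds, and the protocol must be corrected. Both arms have two incompatible injectates, and at least one specification per arm is wrong. Steroid dose differs 1.5-fold (15/10) in the transforaminal arm and 2-fold (80/40) in the catheter arm, lidocaine differs 2-fold in both, and volume differs by 1 mL (2.5 − 1.5) and 1.5 mL (3 − 1.5) respectively. The conflicting text covers all 100 planned participants. That figure counts who is covered, not who would be misdosed.

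If one version is applied consistently, the randomized comparison is sound for that version. The documents do not show that either dose is unsafe, that dosing will be mixed within an arm, or that the primary outcome would change. They also do not show which version was intended. The only assumption in the arithmetic is the lidocaine conversion.

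**What to change.** The sponsor confirms the intended injectate and amends the other section to match.

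- **If the Procedures version is intended,** Study design becomes: Group 1, dexamethasone 1 mL (10 mg/mL) plus 0.5 mL of 1% lidocaine, total 1.5 mL; Group 2, triamcinolone 1 mL (40 mg/mL) plus 0.5 mL of 1% lidocaine, total 1.5 mL.
- **If the Study design version is intended,** the transforaminal procedure becomes 1.5 mL dexamethasone plus 1 mL lidocaine, total 2.5 mL, and the catheter procedure becomes 2 mL triamcinolone plus 1 mL lidocaine, total 3 mL.

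Unless the data collection sheet already captures it, add steroid dose (mg) and total volume (mL) actually given, for each injection, to the items recorded immediately after injection.

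The cost is a short protocol amendment and, only if the sheet lacks it, this added entry per injection. No extra patients, visits or procedures are needed, and the sample size is unaffected.
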